APPENDIX E: SAMPLE COLLECTION METHODS.....		58
APPENDIX F: DSM-5 DIAGNOSTIC CRITERIA FOR AUTISM SPECTRUM DISORDER		59

RESTRICTED DISTRIBUTION OF PROTOCOLS

- This protocol contains information that is confidential and proprietary. The information contained herein is provided for the purpose of conducting a clinical trial in collaboration with [name].
-
- The contents of this protocol may be disclosed to study personnel under your supervision and to your Institutional Review Board(s). The contents of this protocol may not be disclosed to any other parties (unless such disclosure is requested by [name]).

PROTOCOL SYNOPSIS

- Study Drug: L1-79
- Protocol Number: HT 02-121

Protocol Title: A Phase 2 Safety Study of L1-79 in the Treatment of Autism

- Study Phase: 2
- **Study Design:** This study has a dose escalating cohort design. Treatment arms consist of L1-79 at doses of 100 mg t.i.d (or placebo), or 200 mg t.i.d., (or placebo). Pharmacokinetics will be assessed in initial cohorts of 5 patients for each dose group followed by a double blinded, placebo-controlled assessment of PK/PD and safety in a cohort of 15 patients randomized 2:1 active to placebo. Groups 1& 2 below can start simultaneously. While the FDA is reviewing the data from Group 1, Groups 2 and the placebo patients randomized with Group 2 will be ongoing. All 5 subjects assigned to Group 1 (100 mg L1-79) must have completed the PK portion of the study with results analyzed and accepted by the FDA before subjects in Groups 3-5 can begin treatment.
- Sample Size: N=40
 - Group 1 (n=5) 100 mg L1-79 (1x100mg capsule+1 placebo capsule)
 - Group 2 (n=10) 100mg L1-79 (1x100mg capsule+1 placebo capsule)
 - Group 3 (n=5) 200 mg L1-79 (2x100 mg capsules)
 - Group 4 (n=10) 200 mg L1-79 (2x100 mg capsules)
 - Group 5 (n=10) Placebo (2 placebo capsules)

All Groups will receive the assigned study drug three-times daily.

- **Study Population:** Male subjects with autism between the ages of 13 and 21 years of age who meet the entry criteria and who are able to complete standardized measures allowing them to participate in this study.
- **Major Inclusion Criteria:** Males between 13 and 21 years of age, signed informed consent, normal clinical laboratory values, DSM-5 compliant diagnosis of autism spectrum disorder, confirmed by the Autistic Diagnosis Interview Review (ADIR), and by the Autism Diagnosis Observation Schedule (ADOS) score consistent with a diagnosis of autism, no more than one concomitant medication, on a stable regimen for at least 2 weeks prior to enrollment and no planned changes in psychosocial interventions during the trial.

- **Major Exclusion Criteria:** Any co-morbidities, including Fragile-X syndrome, epilepsy, Retts syndrome, ADHD, or other disease or syndrome aside from autism that requires treatment. Any other psychiatric disorder, or out of range lab values. DSM-5 diagnosis of schizophrenia, schizoaffective disorder, alcohol use disorder; active medical problems: unstable seizures (>2 in past month), significant physical illness.
- **Experimental Treatment:** L1-79 at doses of 100, or 200 mg, or placebo 3 times daily for 4 weeks.
- **Non-Experimental Treatment:** Placebo.
- **Dosage and Administration:** L1-79 or placebo, as assigned or as randomized, will be administered orally according to the regimen above.
- **Evaluation Schedule:** Subjects will be evaluated within one week prior to study accession, and weekly throughout the dosing period, and again 4 weeks after the cessation of treatment. The Assigned Dosage Groups (Groups 1 and 3) will have PK blood draws and EKG the randomized group will not have.
- **Safety Measures:** All Groups will have regularly scheduled complete history and physical examination that includes orthostatic blood pressure measurements, vital signs, CBC, differential, platelet counts, urine analysis, serum analytes including: total protein, albumin, glucose, BUN, creatinine, direct and total bilirubin, alkaline phosphatase, phosphorous, calcium, AST, ALT, sodium, potassium, chloride, bicarbonate, T₄, TSH, and adverse events assessments. The Assigned Groups (1 and 3) will also have electrocardiograms taken at the study screening visit and at the week 1.
- **Total Study Duration:** It is expected that the entire study from screening of the first patient until the last patient enrolled has completed the last visit to require a total of 36 weeks. This period was estimated to include an 8 weeks recruitment, 8 weeks for screening, and 8 weeks' for treatment of all patients enrolled in the study and 8 weeks for follow-up.
- **Study Endpoints:** The primary end point will be an assessment of the safety of L1-79 based upon reported adverse events and changes in baseline in physical examination parameters that include orthostatic blood pressure, clinical laboratory measures, and ECGs. Secondary endpoints will include an assessment of pharmacokinetics and pharmacodynamics, as well as the attending physicians assessment as quantified by the Clinical Global Impressions scale based upon

changes from baseline in various psychometric tests, including the Vineland Adaptive Behavior Scale 2nd edition (VABS II, VABS) questionnaire, the Autism Diagnostic Observation Schedule (ADOS), the Aberrant Behavior Checklist-Community (ABC-C), the Spence Anxiety Scale (SAS), the Repetitive Behavior Score – Revised (RBS-R), the Social Responsiveness Scale (SRS), as well as from their personal observations in the clinic, and anecdotally as provided by parents or caregivers over the course of this study.

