3.0 DESIGN AND METHODS

3.1 Study Design

This is a five-arm design that incorporates 2 open label groups whose doses are known for the purpose of understanding PK/PD and to determine if there are any EKG changes associated with the administration of L1-79, and a 3-group prospectively randomized, double-blind, trial of L1-79 at 2 dosage levels versus placebo.

Two dosages of L1-79 will be tested in this study: 100 mg t.i.d. and 200 mg t.i.d. The investigators in this study have the most experience with these two dosages during exploratory use of L1-79 described above. In preliminary observations in a number of patients between the ages of 2.75 and 24 years of age doses between 90 to 400 mg t.i.d. were well tolerated, and no evidence was found that suggests a need for weight based dosing. These findings were presented to the FDA.

The first cohort of 20 patients to be enrolled will all receive L1-79 100 mg t.i.d., and will be comprised of 3 groups of patients. The first 100 mg group will differ from the others in that they will get blood samples drawn for PK analysis and EKGs will be taken. The safety and PK data from this group will be submitted for FDA review and acceptance before the 200 mg t.i.d. cohort will be enrolled. The remaining 15 patients in this cohort will be randomized to receive either L1-79 100 mg t.i.d. or placebo on a 2:1 basis (2 L1-79 patients for each placebo patient). While the FDA is reviewing the data from the first 5 patients all 100 mg t.i.d. patients will continue to be treated.

The second cohort is identical to the first. The initial 5 patients to be enrolled will differ from the others in that they will get blood samples drawn for PK analysis and EKGs will be taken. The safety and PK data from this group will be submitted for FDA review and acceptance. The remaining 15 patients in this cohort will be randomized to receive either L1-79 200 mg t.i.d. or placebo on a 2:1 basis (2 L1-79 patients for each placebo patient). While the FDA is reviewing the data from the first 5 patients all enrolled patients will continue to be treated

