5.1.3 RANDOMIZED GROUP

Following the enrollment of 5 open label patients as described in the Assigned Dosage Groups, an additional 15 patients at each dose level will be randomized 2:1 to receive either active drug or placebo (2 active to each placebo patient. These patients will be treated identically to those in the Assigned Dosage Groups with 3 exceptions:

1. No pharmacokinetic samples will be drawn,
2. No EKG will be performed
3. They will not have the 1 week follow-up, just the 1 month follow up.

After being randomized to a treatment arm each patient will be assigned a study number comprised of a 2-digit site identifier and a 3-digit patient identifier as described above.

Study numbers will not be assigned until a patient is qualified and entered into the trial. Screening failures will not be assigned numbers. However, a list of screen failures and their demographic data will be maintained by the Investigator.

Patients will be enrolled and receive their first dose within 3 weeks of completing the screening procedure.

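### The synopsis start rule holds back all 10 placebo patients until the 100 mg PK review, contradicting the sentence before it and the sections that hold back only the 200 mg cohort or dose

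*Combined protocol and SAP*

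**What the plan says.** The Protocol Synopsis lists five groups of 5, 10, 5, 10 and 10 patients. Groups 1 and 2 receive 100 mg, Groups 3 and 4 receive 200 mg, and Group 5 is the only placebo group. It is not divided by cohort. The start rule requires that the Group 1 PK results be analysed and gain FDA acceptance "before subjects in Groups 3-5 can begin treatment". The sentence immediately before says that, while that review runs, "Groups 2 and the placebo patients randomized with Group 2 will be ongoing".

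Other sections describe the allocation and the hold differently:

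- **Section 3.1**, on the 100 mg cohort: "The remaining 15 patients in this cohort will be randomized to receive either L1-79 100 mg t.i.d. or placebo on a 2:1 basis". The 200 mg cohort follows the same pattern. Only the 200 mg cohort waits for the FDA.
- **Section 4.3** releases 20 further patients once permission to escalate is given.
- **Section 5.1.1** restricts only doses above 100 mg.
- **Section 5.1.3** repeats the 2:1 randomisation of 15 patients at each dose level.
- **Section 5.9.3.3** makes a favourable review a condition for enrolling the 200 mg group.

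On start order, the synopsis says "Groups 1& 2 below can start simultaneously". Section 5.1.3 introduces the randomised patients with the words "Following the enrollment of 5 open label patients as described in the Assigned Dosage Groups".

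**The concern.** The placebo patients randomised alongside Group 2 can only be members of Group 5, because no other placebo group exists. The synopsis therefore says of the same patients both that they are on study during the review and that they may not yet start.

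A site, or whoever prepares the randomisation list, might work from the synopsis alone. Patients starting in the randomised part of the 100 mg cohort before acceptance would then all be on active drug. Anyone who knew the rule could infer allocation from the start date, and the 100 mg patients would have no placebo patients treated alongside them in that period. The main efficacy measure is the investigator's CGI judgement (Sections 3.2.2.1 and 6.1.5.1), which is exposed both to loss of blinding and to raters shifting over time.

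Other text also treats placebo as one undivided arm. Section 6.1.5.1 plans comparisons with a single placebo arm. Section 5.1.4 gives rollover patients the dose their group had been receiving, which an undivided Group 5 does not define.

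**Working it through.** **Reproducing the stated sizes.** From Sections 3.1 and 5.1.3, each cohort has 5 open-label and 15 randomised patients.

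- Active per cohort: 15 × 2/3 = 10. Placebo per cohort: 15 × 1/3 = 5.
- Total: 2 × (5 + 15) = 40, the synopsis N.
- Placebo: 2 × 5 = 10, the synopsis Group 5.

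The synopsis sizes therefore agree with the body only if 5 of the 10 Group 5 patients belong to the 100 mg cohort.

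**Counting who may start before FDA acceptance.**

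| | Synopsis rule, read literally | Sections 3.1 and 4.3 |
|---|---|---|
| May start | 5 + 10 = 15 | 5 + 15 = 20 |
| of whom placebo | 0 | 5 |
| Held back | 5 + 10 + 10 = 25 | 5 + 15 = 20 |
| of whom placebo | 10 | 5 |
| Active share among randomised patients who may start | 10/10 = 100% | 10/15 = 67% |

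The gap of 25 − 20 = 5 is exactly the first-cohort placebo patients. Sections 5.1.1 and 5.9.3.3 do not restrict those patients either.

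**Effect on the 100 mg v placebo contrast.** Suppose ratings shift by d between the two cohort periods. The documents give no value for d, so it stays a symbol.

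- All placebo treated in the later period (the extreme of the literal rule): bias of size d.
- Placebo pooled across cohorts, 5 + 5: the placebo mean moves by (5 × 0 + 5 × d)/10 = d/2, so the bias has size d/2.
- Placebo from the same cohort only: bias 0.

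**Precision, in units of the outcome SD.**

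- Within cohort, 10 v 5: √(1/10 + 1/5) = √0.30 = 0.55.
- Pooled placebo, 10 v 10: √(1/10 + 1/10) = √0.20 = 0.45.
- Ratio: √(0.30/0.20) = 1.22, so the within-cohort SE is about 22% larger.

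Each dose occurs in one cohort only. A model with a cohort term therefore gives the same within-cohort contrast and the same 0.55.

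**The case against.** The strongest reply is that nobody would run the trial on the literal rule. The adjoining sentence has first-cohort placebo patients on study, and four body sections hold back only the 200 mg cohort or dose. Section 7.3 says that neither investigator nor sponsor knows a patient's group, so they could not hold back only the placebo patients without breaking the blind. This stands: the likely explanation is a group-numbering slip, and the harm is conditional on someone following the synopsis alone. It does not remove the contradiction.

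A reader might go further and infer that the 100 mg cohort has no placebo at all and is unblinded by design. The documents do not support that. Even on the literal reading the 5 placebo patients are delayed, not removed, and Section 3.1 randomises within that cohort. That section does open by saying that all 20 first-cohort patients receive 100 mg, but the same paragraph goes on to randomise 15 of them to 100 mg or placebo.

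A reader might also infer that nothing settles who goes open label and who is randomised, since Groups 1 and 2 may start together. Section 5.1.1 answers this: the first 5 are open label and the next 15 are randomised. Section 5.1.3 asks only that the 5 open-label patients have been enrolled, not that they have finished. The word used for the joint start is loose, and no more.

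It is also fair to say that no section prescribes pooling placebo across cohorts, that Section 6.1 makes the analysis descriptive and leaves a formal plan for later, and that safety is the primary endpoint. The drift argument is therefore a reason to specify the comparison in that plan. It does not show an error in a written analysis.

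**Conclusion.** The synopsis start rule is wrong as written. It holds 25 patients, including all 10 on placebo, where Sections 3.1 and 4.3 hold 20, and it contradicts its own preceding sentence. This part is counting and needs no assumption.

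The consequence is conditional. If the rule were followed literally, the 15 patients allowed to start before acceptance would all be on active drug, the 100 mg cohort would lack concurrent placebo in that period, and start date would reveal allocation. The surrounding text suggests that the intended hold covered only the 200 mg cohort and its own placebo patients, but the sponsor must confirm this.

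The bias figures (up to d, d/2 and 0) assume a shift in ratings between cohorts whose size is undocumented. They show which comparison is protected, not how much harm to expect. The SE figures assume a common SD and full enrolment.

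**What to change.** 1. Reconcile the synopsis start rule with the sentence before it and with Sections 3.1, 4.3, 5.1.1 and 5.9.3.3, so that one rule states which patients wait for FDA acceptance.
2. Show Group 5 as two sets of 5 placebo patients, one randomised with Group 2 and one with Group 4, and use those labels in the start rule. N stays 40 and placebo stays 10.
3. In the statistical plan still to be written, present each dose against the placebo patients randomised in the same cohort, or stratify by cohort. Show pooled placebo as supportive.
4. As a minor wording point, align the synopsis statement on the joint start of Groups 1 and 2 with Sections 5.1.1 and 5.1.3.

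Items 1, 2 and 4 are wording changes. Item 3 has a real cost with only 5 placebo patients per cohort: an SE of 0.55 SD instead of 0.45 SD, about 22% larger. That is the price of a comparison unaffected by drift between cohorts, and the supportive pooled display keeps the more precise figure in view.

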1.0 INTRODUCTION AND RATIONALE

L1-79 is being developed for the treatment of autism. Dr. [name] holds IND 128673 and is also one of the Principal Investigators. Yamo Pharmaceuticals LLC, a part of Hoffman Technologies is providing support and L1-79 for the study.

L1-79 is racemic α -methyl-para-tyrosine (AMPT). This molecule was developed by Merck in the 1950's & 60's. The L-isomer was approved in 1979 as a presurgical treatment for the excision of pheochromocytoma tumors under the tradename Demser[®]. Because pheochromocytomas produce high levels of catecholamines, surgical manipulation of these masses liberates substantial concentrations of epinephrine and norepinephrine resulting in adverse cardiovascular events. Demser inhibits the first, and rate limiting, step in catecholamine synthesis, the conversion of tyrosine to dihydroxyphenylalanine (DOPA), and thus reduces the synthesis of dopamine (DA), norepinephrine (NE), and epinephrine (E). This inhibition has the effect of reducing tissue catecholamine levels making the tumor more amenable to extirpation without adverse consequences. Demser has also been approved for the treatment of subjects with pheochromocytoma for whom surgical excision is not an option to reduce the cardiovascular consequences of elevated levels of circulating catecholamines.

Catecholaminergic functions in the CNS and in the gut have been implicated as underlying the symptoms of autism. In the brain, dopaminergic systems have been shown to underlie systems that mediate pleasure, irritability, agitation, reward, and other symptoms that characterize autism. In the gut and mesentery, catecholaminergic systems are known to modulate digestion, and may underlie the digestive and dietary abnormalities associated with autism.

L1-79 has been used in a 30 patient phase 1 trial as one agent in the polytherapy named SM-88 (previously called SMK) (J Clin Oncol 31, 2013 suppl; abstr e22095). L1-79 was used at a dosage of 280 mg/d, along with daily 3-Amino-2-hydroxy-4-phenylbuteryl]-L-leucine (55 μ g/d), phenytoin (32 mg/d), melanin (50 μ g/d), and the melanin inducer melanotan II (10 μ g/d) (IND #127977). In this regimen, L1-79 was administered to stage 4 metastatic cancer patients with a variety of tumor types including breast, prostate, pancreas, colon, lung, appendix, and others, who had failed all available therapeutic regimens.

An exploratory study intended to observe the effects of L1-79, when administered to patients with autism spectrum disease, was initiated at two sites in New Jersey. L1-79 was given to 10 patients to date on a t.i.d. schedule. Preliminary results indicated that L1-79 reduced the core deficits in a number of subjects, with the racemic form of the drug being more effective than either of the two stereoisomers alone. Utilizing the Aberrant Behavior Checklist – Community (ABC-C), Autism Diagnostic Observation Scale (ADOS), and Connor Parent Rating Scale (CPRS), improvements in all of the core symptoms of autism have been observed to occur quickly in subjects of both sexes and

ranging in age from 2½ to 24 years of age, with continual improvement with treatment over time.

Most of the clinical experience with L1-79 for the treatment of autism is with doses of 100-300 mg t.i.d.. This study seeks to quantify the safety and efficacy of L1-79 administered t.i.d. in doses of 100 or 200 mg to subjects with a diagnosis of autism based upon their ADOS results in a prospectively randomized and double-blind manner.

2.0 STUDY PURPOSE AND OBJECTIVES**2.1 Purpose**

The purpose of this clinical trial study is to determine whether L1-79 is a well-tolerated and clinically useful agent for the treatment of ASD, and to assess the pharmacokinetics and pharmacodynamics of 4 weeks of t.i.d. dosing with L1-79.

2.2 Study Objectives**2.2.1 PRIMARY OBJECTIVE**

To document the safety of L1-79 by assessing adverse events, electrocardiographic and physical examination measures, including vital signs and laboratory parameters at 2 different dose levels of L1-79.

2.2.2 SECONDARY OBJECTIVES

To document the PK and PD of L1-79 in a repeated dosing clinical situation, and to assess any change from baseline in the core symptoms of autism and associated behaviors using various standardized, validated ASD assessment instruments, and by comparing the results of subjects randomized to receive 1 of 3 different dosage levels of L-79 against placebo in a double-blind fashion. Also, changes in the ADOS core, including the severity scale, and the Clinical Global Impressions scale (CGI), including severity and improvement subscales will be assessed.

3.0 DESIGN AND METHODS

3.1 Study Design

This is a five-arm design that incorporates 2 open label groups whose doses are known for the purpose of understanding PK/PD and to determine if there are any EKG changes associated with the administration of L1-79, and a 3-group prospectively randomized, double-blind, trial of L1-79 at 2 dosage levels versus placebo.

Two dosages of L1-79 will be tested in this study: 100 mg t.i.d. and 200 mg t.i.d. The investigators in this study have the most experience with these two dosages during exploratory use of L1-79 described above. In preliminary observations in a number of patients between the ages of 2.75 and 24 years of age doses between 90 to 400 mg t.i.d. were well tolerated, and no evidence was found that suggests a need for weight based dosing. These findings were presented to the FDA.

The first cohort of 20 patients to be enrolled will all receive L1-79 100 mg t.i.d., and will be comprised of 3 groups of patients. The first 100 mg group will differ from the others in that they will get blood samples drawn for PK analysis and EKGs will be taken. The safety and PK data from this group will be submitted for FDA review and acceptance before the 200 mg t.i.d. cohort will be enrolled. The remaining 15 patients in this cohort will be randomized to receive either L1-79 100 mg t.i.d. or placebo on a 2:1 basis (2 L1-79 patients for each placebo patient). While the FDA is reviewing the data from the first 5 patients all 100 mg t.i.d. patients will continue to be treated.

The second cohort is identical to the first. The initial 5 patients to be enrolled will differ from the others in that they will get blood samples drawn for PK analysis and EKGs will be taken. The safety and PK data from this group will be submitted for FDA review and acceptance. The remaining 15 patients in this cohort will be randomized to receive either L1-79 200 mg t.i.d. or placebo on a 2:1 basis (2 L1-79 patients for each placebo patient). While the FDA is reviewing the data from the first 5 patients all enrolled patients will continue to be treated

Adolescents, between the ages of 13 and 21 years, with ASD who meet the entry/exclusion criteria, and with sufficiently high function to complete this study in the opinion of the Investigator, will be treated daily for 4 weeks. Standard psychometric tests will be utilized in the clinic and at home to ascertain affect and performance in order to assess changes in the symptoms and the diagnosis of autism.

Enrollment will be limited to male patients pending FDA approval and the completion of reproductive toxicology studies.

